5.5. Evaluations and data collection in CRF

5.5.1. Demographics

Demographic data and other baseline characteristics will be obtained and recorded at screening.

5.5.2. Medical history and medications

Medical history, only ongoing drug treatments for the underlying disease, and recently completed immunosuppressive treatment (i.e., <4 weeks from inclusion) are recorded at the screening visit. Ongoing immunosuppressive treatments are divided into steroid and non-steroid treatments.

Specific treatments for individual patient groups are recorded at the screening visit as follows:

Patient group	Parameter
Patients with HIV infection	Antibiotic treatment during the last 3 months.
Patients who have undergone solid organ transplantation	Rejection treatment during the last 6 months. Thymoglobulin treatment during the last 12 months. Rituximab treatment during the last 12 months. Chemotherapy during the past 12 months.
Patients with CLL	Fludarabine (/cyclophosphamide (FC) in combination with rituximab (FCR) during the last 6-30 months. Bedamustine in combination with rituximab (BR) within the last 6-30 months. Rituximab-containing treatment during the last 6 months.

All new medications during the period from the vaccination date to 14 days after each vaccine dose are recorded (i.e., both after vaccine dose 1 and vaccine dose 2). The rationale for this time limit is that if certain adverse events occur during the AE observation period, an assessment must be made as to whether they are related to the study drug or another medication. Although no interaction studies have been conducted in previous clinical trials, we do not expect any drug interactions between the study drug and other drugs. We have already excluded individuals who are scheduled to receive any other vaccination in the exclusion criteria. However, any newly initiated immunosuppressive or immunoglobulin treatments after day 0 (screening) will be recorded, as this may affect the efficacy of the vaccine.

5.5.3. Reactogenicity (Diary)

Each study participant will be provided with a diary. Study participants will record and rate the severity of symptoms in a diary according to 5.8.3. The evaluation will take place from the day of vaccination until 7 days after the dose, after each vaccine dose.

A reactogenicity event recorded in the diary will not be recorded as an AE unless it meets the criteria for an SAE.

5.5.4. Adverse events

Please refer to sections 5.7 and 5.9.

5.5.5. Targeted and symptom-driven physical examination

Examination of various organs/systems indicated by signs or symptoms reported by the study participant and clinically indicated will be performed according to schedule or between/after study visits during the study period.

Any clinically significant change in the findings of the physical examination will be recorded as an AE, unless the event is due to an existing medical condition or is due to treatment given for the existing medical condition.

5.5.6. Vital parameters

At the times specified in the schedule (Table 2), systolic and diastolic blood pressure, pulse, temperature, and respiratory rate will be measured and recorded. Any clinically significant abnormal vital sign value will be recorded as an AE, unless it is deemed not to be due to an existing medical condition or treatment given for the existing medical condition.

5.5.7. Clinical laboratory tests

The predefined safety samples according to 5.2 will be taken and recorded. Any abnormal sample value that is considered clinically significant by the investigator should be recorded as an AE, unless it is due to an existing medical condition or is due to treatment given for the existing medical condition.

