5.7. Definitions of adverse events

5.7.1. Incident/Adverse event (AE)

Any incident (AE), or worsening of an existing medical condition in a research subject who has received an investigational drug, regardless of whether it is causally related to the treatment or not, i.e., it may be an adverse and undesirable sign (including an abnormal laboratory finding), symptom, or disease that is temporally associated with the use of an investigational medicinal product, regardless of whether it is related to the investigational medicinal product or not.

However, events that are an expected consequence of the underlying disease, such as worsening of the underlying disease, will not be reported as an AE. This is because we do not expect Comirnaty to affect the progression of the underlying disease.

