5.9. Reporting of adverse events

5.9.1. Reporting of adverse events (AE)

- All adverse events should be recorded in a special AE form in the CRF for the period from the day of the first and second vaccine doses until 14 days after each vaccine dose. Exceptions are adverse events that are an expected consequence of the underlying disease, such as worsening of the underlying disease.
- Rationale for the above point: In Phase I and Phase II/III studies of Comirnaty, AEs were collected for the period from informed consent to one month after the second dose. As this has already been studied in approximately 21,000 people with a favorable safety profile, and we do not expect multiple AEs or autoimmune reactions in immunosuppressed individuals, the observation periods are limited to those above. As we expect frequent medical events of a non-serious nature in the majority of the included primary population due to the existing medical condition, such events are excluded from data collection.

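### Sections 5.5.5 and 5.5.7 keep findings due to background treatment out of the AE count, while 5.7.1, 5.8.2 and the first bullet of 5.9.1 would count them; the difference falls almost only on patients

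*Combined protocol and SAP*

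**What the plan says.** The rule for what becomes an AE is stated in several places in the combined protocol and SAP.

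- **5.5.7 (laboratory tests):** a clinically significant abnormal value is an AE "unless it is due to an existing medical condition or is due to treatment given for the existing medical condition".
- **5.5.5 (physical examination):** a clinically significant change is an AE "unless the event is due to an existing medical condition or is due to treatment given for the existing medical condition".
- **5.7.1 (definition):** an AE is any incident "or worsening of an existing medical condition in a research subject who has received an investigational drug, regardless of whether it is causally related". Abnormal laboratory findings are named as included. The one exception is that "events that are an expected consequence of the underlying disease, such as worsening of the underlying disease, will not be reported as an AE".
- **5.9.1, first bullet (reporting):** "Exceptions are adverse events that are an expected consequence of the underlying disease, such as worsening of the underlying disease".
- **5.9.1, second bullet (rationale):** non-serious events are expected to be frequent in most patients, and where they are "due to the existing medical condition, such events are excluded from data collection".
- **5.8.2 (causality):** every AE is graded. The possible and unlikely grades both provide for events that other medicines or the underlying disease can explain.

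The proportion with AEs is a secondary endpoint (4.2), analysed in the full analysis set and compared with controls (6.3.3). Controls must have no immunosuppressive disease or treatment and no significant co-morbidity (5.1.3, criterion 2b).

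**The concern.** The exceptions do not have the same scope. Sections 5.5.5 and 5.5.7 leave out findings caused by treatment for an existing condition; 5.7.1 and 5.9.1 never mention treatment. For findings caused by the condition itself, the sections differ on whether the consequence must be expected, and on whether the condition is the underlying disease or any existing one.

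The compared groups differ in exactly the feature on which the wider exception acts. Many patients take long-term treatment for their inclusion diagnosis, and controls by definition take no immunosuppressive treatment. An investigator who follows 5.5.7 and one who follows 5.7.1 would report different AE proportions from the same patients, but nearly the same proportion in controls. At stake is whether the between-group AE difference has one definition.

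**Working it through.** The plan states no figure for this point, so there is none to reproduce. The check is a comparison of text, followed by a look at how often the conflict can arise.

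**Step 1. Classify a clinically significant finding by cause.**

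| Finding due to | 5.5.5 / 5.5.7 | 5.7.1 | 5.9.1, bullet 1 | 5.9.1, bullet 2 (non-serious) |
|---|---|---|---|---|
| Expected consequence of underlying disease | not AE | not AE | not AE | not collected |
| Unexpected consequence of underlying disease | not AE | AE | AE | not collected |
| Another existing condition | not AE | AE | AE | depends on what existing condition means |
| Treatment for an existing condition | not AE | AE | AE | not named, so AE |

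The first row shows no conflict. The second and third are inconsistent, but 5.9.1 is itself divided or unclear on them. The fourth is the firm conflict: no reading of 5.7.1 or 5.9.1 supplies a treatment exception.

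**Step 2. Look for the intended order of recording and attribution.** Section 5.8.2 can grade an event that other drugs explain only if the event has been recorded. Section 5.5.2 justifies listing new medication in the 14 days after each dose by the need to judge whether an AE comes from the study drug or another medicine. Both put attribution to drugs after recording, whereas the clause in 5.5.5 and 5.5.7 puts it before.

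**Step 3. Direction.** Dropping treatment-attributed findings can only lower a group's AE proportion. Appendix 1 has fields for controls' diagnoses and medicines, so their loss need not be exactly zero, but criterion 2b keeps it close to zero.

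**Step 4. Opportunity.** AEs are collected from the day of each dose to 14 days after it (5.9.1). Scheduled safety draws after the first dose are:

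- Day 21 ± 3, which is 18 to 24 days after dose 1 and so past that window. It shares a date with dose 2 but is taken before the injection.
- Two weeks ± 3 days after dose 2: 14 − 3 = 11 to 14 + 3 = 17 days. Days 11 to 14 are inside the window and days 15 to 17 outside, so 4 of the 7 permitted days count.

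Examinations are symptom-driven only (5.3.2, 5.5.5), with no fixed number.

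**Step 5. Scale.** Let f be the share of patients whose only AE is a treatment-attributed finding. The patient proportion moves by f and the control proportion by about 0. One such patient moves the pooled proportion by 1/450 = 0.22 points, or one diagnosis group by 1/90 = 1.11 points. The documents give neither f nor any AE rate. As a yardstick only, assume an AE proportion p of 20% to 40%, with SE = √[p(1 − p)(1/n₁ + 1/n₂)]:

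- 450 v 90: √(0.16 × 0.01333) = 4.6 points, to √(0.24 × 0.01333) = 5.7 points.
- 90 v 90: √(0.16 × 0.02222) = 6.0 points, to √(0.24 × 0.02222) = 7.3 points.

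A shift of one pooled SE would need about 21 to 25 of the 450 patients (450 × 0.0462 = 20.8; 450 × 0.0566 = 25.5). Nothing in the documents says whether the true number is near that.

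**The case against.** A good part of the opposing case stands.

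- **5.9.1 already excludes much of this.** Its second bullet removes non-serious events due to the existing condition, which is close to the first half of the exception in 5.5.5 and 5.5.7. That bullet also uses existing condition to justify an exception worded as underlying disease, so the two terms may mean the same thing. A reader might infer that 5.9.1 clearly counts worsened co-morbidities; it does not. The firm conflict narrows to treatment.
- **5.7.1 also needs a judgement before recording.** Deciding that an event is an expected consequence of the disease is itself attribution, and it too removes events only from patients. Removing the treatment clause reduces the asymmetry but does not end it.
- **A governing section is indicated.** Section 5.5.4 refers adverse events to 5.7 and 5.9. It does not say that they override the more specific 5.5.5 and 5.5.7, so the ambiguity remains.
- **The data are not lost.** Safety samples are recorded whether or not they become AEs (5.5.7), 6.3.1 plans a description of abnormal findings, and SAEs have their own definition without a treatment clause (5.7.2, 5.9.2). A reader might infer that the wording hides vaccine harm or secures a finding of no added risk. The documents do not support that, and no non-inferiority conclusion on safety is planned.
- **The size has no anchor.** It is tempting to assume that 5% to 20% of patients are affected and to compute the power lost. No AE rate supports such a range. An excess made up wholly of treatment-attributed findings would also be largely background morbidity set against healthy controls, not a vaccine effect.

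**Conclusion.** The inconsistency is real and should be corrected. Its firm part is the treatment clause in 5.5.5 and 5.5.7, which conflicts with 5.7.1, with the first bullet of 5.9.1 and with the purpose of 5.8.2. The differing wording for condition-caused events is a secondary inconsistency, partly inside 5.9.1.

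The direction follows from eligibility: if the clause is applied, the AE proportion falls in patients and hardly at all in controls. The size is unknown. It may be small, given one post-dose laboratory draw that falls only partly in the window, a pre-injection draw on the day of dose 2, and examinations made only for symptoms. This rests on investigators applying 5.5.5 and 5.5.7 as written; the documents do not say which section was followed in practice.

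**What to change.** Reconcile 5.5.5, 5.5.7, 5.7.1 and both bullets of 5.9.1 into one AE rule, stated once and cross-referenced.

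1. Keep at most the exception for expected consequences of the underlying disease, and define that as the inclusion diagnosis.
2. Remove the treatment clause from 5.5.5 and 5.5.7. An abnormality unchanged from the screening or day 0 value is neither a new incident nor a worsening, so the clause is not needed to keep stable values out.
3. Record attribution to concomitant treatment in the 5.8.2 causality field.
4. In 6.3.3, report AEs overall and by causality, for patients and controls.
5. For AEs already collected, state which rule was applied. Add a sensitivity analysis that counts recorded post-dose laboratory abnormalities by a criterion fixed beforehand and identical in both groups.

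Section 5.5.6 should be read in the same pass: its exception for vital signs ("unless it is deemed not to be due to an existing medical condition or treatment given for the existing medical condition") runs the opposite way as written, which is a separate defect.

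The cost is mainly wording, since baseline values and the causality field exist. There will be somewhat more AE entries in the patient groups, some reflecting background treatment rather than the vaccine. For participants whose AE windows have closed (section 2.1 already reports results up to 12 months), new wording cannot recover unrecorded AEs. The laboratory sensitivity analysis covers only part of that gap and does not reach unrecorded examination findings.

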5.5.8. Pregnancy test

A urine test will be performed on all women of childbearing age and the results will be recorded.

5.5.9. Serum SARS-CoV-2 serology

Test results, whether positive or negative, will be recorded for samples taken according to the schedule in Table 2, and the results will be communicated to study participants verbally or by letter. However, this test cannot distinguish between the presence of antibodies after vaccination or SARS-CoV-2 infection. Samples are planned to be analyzed at Clinical Microbiology, Karolinska University Hospital (an accredited and validated laboratory) according to standard healthcare procedures. If a method for quantitative measurement of antibodies has been established at this laboratory, antibody titers will also be noted in addition to positive or negative results.

5.5.10. Diagnosis of SARS-CoV-2 positivity/COVID-19

Study participants who have been diagnosed with positive SARS-CoV-2 or COVID-19 within healthcare are registered with the date and symptoms. COVID-19 severity is graded according to section 5.3.5.

5.6. Investigational medicinal products

5.6.1. Description of investigational medicinal products

Comirnaty: Concentrate for solution for injection, dispersion (sterile concentrate). The vaccine is a white to off-white frozen dispersion (pH: 6.9-7.9).

Comirnaty is administered intramuscularly after dilution with sodium chloride as a vaccination series consisting of 2 doses (0.3 ml each) at least 21 days apart. Sodium chloride will be ordered from the hospital pharmacy according to clinical routine.

5.6.2. Labeling and handling of investigational medicinal products

The vaccine is distributed via Region Stockholm. The vaccine will be handled and administered at the respective clinics. Therefore, no study-specific labeling of the investigational medicinal product will be done.

The investigational medicinal product will be stored until vaccination in accordance with the instructions in the summary of product characteristics.

5.6.3. Method of administration

Comirnaty will be prepared by healthcare professionals using aseptic technique to ensure that the prepared dispersion is sterile. Thawing and dilution will be performed according to the summary of product characteristics. Intramuscular administration of Comirnaty is planned to take place at

study unit. Close observation for at least 30 minutes after vaccination for people with bleeding disorders. Other study participants will be observed for at least 15 minutes after vaccination. Those who have experienced an anaphylactic reaction after the first dose will not receive a second dose of the vaccine.

5.6.4. Traceability and compliance with treatment

Administration of the investigational medicinal product will be documented at each unit with information such as who administered the product, the research subject, date, time, and batch number. Any remaining investigational medicinal product will be destroyed at each clinic.

5.6.5. Concomitant use of other drugs

All simultaneous use of other drugs will be documented in the CRF.

5.6.6. Treatment after the end of the study

After the end of the study, patients will receive treatment according to clinical routine.

5.7. Definitions of adverse events

5.7.1. Incident/Adverse event (AE)

Any incident (AE), or worsening of an existing medical condition in a research subject who has received an investigational drug, regardless of whether it is causally related to the treatment or not, i.e., it may be an adverse and undesirable sign (including an abnormal laboratory finding), symptom, or disease that is temporally associated with the use of an investigational medicinal product, regardless of whether it is related to the investigational medicinal product or not.

However, events that are an expected consequence of the underlying disease, such as worsening of the underlying disease, will not be reported as an AE. This is because we do not expect Comirnaty to affect the progression of the underlying disease.

5.7.2. Serious incident/Serious adverse event (SAE)

Any incident that:

- results in death
- is life-threatening
- requires hospitalization or prolongs hospitalization
- causes permanent or significant disability or impairment
- results in a congenital injury/malformation
- is serious for other reasons as described below

Medical and scientific judgment should be used to determine whether an event is "serious" and whether it would be reportable in other situations, such as important medical events that may not be directly life-threatening or result in death or hospitalization, but may jeopardise the research subject or may require intervention to prevent one of the other outcomes listed in the definition above. These should also be considered SAEs.

However, events that are an expected consequence of the underlying disease, such as worsening of the underlying disease, will not be reported as SAEs. This is because we do not expect Comirnaty to affect the progression of the underlying disease.

Hospitalization due to day surgery, elective surgery, or admission that was planned before the start of the study for a pre-existing medical condition that has not worsened

is not considered an SAE.

The investigator is responsible for assessing the severity (serious or non-serious). If the incident is considered serious, it should be reported as a serious adverse event (SAE) by the investigator to the sponsor.

5.7.3. Suspected unexpected serious adverse reactions (SUSAR)

An adverse reaction/event that is serious, unexpected, and suspected to be caused by the treatment, i.e., adverse reactions that are not previously described (in the summary of product characteristics).

5.8. Assessment of adverse reactions

5.8.1. Assessment of severity

Each incident should be classified by the investigator as mild, moderate, or severe.

- Mild: The event is relatively mild and transient in nature but does not affect the normal life of the research subject.
- Moderate: The event causes functional impairment but does not affect health. The event may be sufficiently unpleasant and interfere with normal activities but does not completely prevent them.
- Pronounced: The event causes impairment of function or working capacity or poses a health risk to the research subject.

5.8.2. Assessment of causality

The investigator is responsible for determining whether there is a causal relationship between the AE/SAE and the use of an investigational medicinal product. AEs suspected of being related to the investigational medicinal product will be followed up until the research subject has recovered or is well cared for and on the road to recovery. All AEs should be categorized as either probably related, possibly related, or probably unrelated according to the definition below:

- Probable: Clinical event, including abnormal laboratory tests, occurring within a reasonable time after administration of the intervention/study product. Unlikely to be attributable to underlying disease or other drugs.
- Possible: Clinical event, including laboratory tests, occurring within a reasonable time after administration of the intervention/study product. The event can be explained by the investigational medicinal product and its occurrence is reasonable in connection with the use of the investigational medicinal product, but there is insufficient information to establish the connection. The event can be explained by underlying disease or other medicinal products.
- Unlikely: Clinical event, including abnormal laboratory test results, but not reasonable in relation to the use of the intervention/investigational product. The event is unlikely to be related to the intervention/investigational product and can be explained by other drugs or underlying disease.
- Not classifiable: The event cannot be classified due to lack of information or because the event is not verified.

5.8.3. Assessment of local and systemic reactogenicity

1.1.1.3 Assessment of local reaction at the injection site

The occurrence of pain, redness, and swelling at the injection site is reported in a diary completed by the patient for the period from the vaccine dose to 7 days after the dose for both the first and second vaccine doses. Local bleeding is observed by staff after injection during the observation period. For individuals who have difficulty filling in a diary, study staff will contact the patient on days 2 and 7 after the vaccine dose to collect data by telephone.

The rationale for the 7-day period after the vaccine dose is that local reactions have been studied in 8,183 study participants within 7 days after injection, and these reactions usually began within two days after vaccination and disappeared after 1-2 days. Only 1% reported severe pain, and a lower frequency was reported for redness or swelling. These reactions were less common in people over 55 than in younger people. We do not expect a higher frequency or more severe degree of these local reactions, possibly the opposite in immunosuppressed individuals. An exception may be local bleeding at the injection site, due to existing medical conditions with coagulopathy or anticoagulant treatments.

Table 1. Local Reaction Grading Scale

	Mild (Grade 1)	Moderate (Grade 2)	Severe (Grade 3)	Potentially Life Threatening (Grade 4)
Pain at the injection site	Does not interfere with activity	Interferes with activity	Prevents daily activity	Emergency room visit or hospitalization for severe pain
Redness	>2.0 cm to 5.0 cm (5 to 10 measuring device units)	>5.0 cm to 10.0 cm (11 to 20 measuring device units)	>10 cm (≥ 21 measuring device units)	Necrosis or exfoliative dermatitis
Swelling	>2.0 cm to 5.0 cm (5 to 10 measuring device units)	>5.0 cm to 10.0 cm (11 to 20 measuring device units)	>10 cm (≥ 21 measuring device units)	Necrosis

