Study visits		X	X	X	X		X	X	X	X	X	X	X	X
Review of health declaration questions in Vaccinate and/or registration in Vaccinate			X		X			X	X	X	X	X	X	X
Sampling of clinical laboratory samples	X ¹	(X) ^{1,2}		X _{1,2}	X ¹									
SARS-CoV-2 sampling serology and humoral immunity (blood and saliva)		X ²	X	X ²	X		X ³	X	X	X	X	X	X	X
Sampling for cellular immunity analyses (blood)		X ²	X	X ²	X		X	X	X	X	X	X		X ¹⁴

Visit no.	Screening	1	2	3	4	5	6	7	8	9	10	11	12	13
Study contacts		d 0	10 d FU (vacc 1)	d 21	2 v FU (vacc 2)	6v FU (vacc 2)	3 months FU (vacc 2)	6 months FU (vacc 2)	9 months FU (vacc 2)	12 months (vacc 2)	18 months (vacc 2)	24 months (vacc 2)	30 months (vacc 2)	36 months (vacc 2)
Time span	0-28 days before visit 1	Day 0	+/-3 days	+/-3 days	+/-3d	+/-3d	+/- 2 w	+/- 3v	+/- 3v	+/- 3v	+/- 3v	+/- 3v	+/- 3v	+/- 3v
Other procedures for both sampling groups A and B														
Informed consent	X								X				X	
Inclusion/exclusion criteria	X	X												
Demographics	X													
Concomitant medication⁴	X	X	X	X	X	X	X	X	X	X	X	X	X	X
Symptom-driven physical examination⁵														
Vital signs⁶		X		X										
15/30 min post-vaccination observation period		X		X										
Handing out of diary		X		X										
Review of diary for local and systemic reactogenicity⁷			X		X									
Collection AE⁸			X	X	X									
Collection SAE/SUSAR⁹			X	X	X	X								
Sampling SARS-CoV-2 PCR test		X ^{2,10}												
Pregnancy test for women of childbearing age (urine)	X ¹¹	(X) ¹¹												
Microbiome samples for HIV-infected individuals and control subjects, if they have agreed to this part (fecal sample)	X ¹²											X ¹²		X ¹²
For HIV-infected individuals, HIV DNA sample	X ¹³	(X) ¹³					X	X	X	X	X	X	X	X
For HIV-infected individuals, HIV RNA test	X ¹³	(X) ¹³		X	X		X	X	X	X	X	X	X	X
Note any additional vaccination with Comirnaty								X	X	X	X	X	X	X
Question about Covid 19								X	X	X	X	X	X ¹⁵	X ¹⁵

Abbreviations: d= day; w= week; m= month; vac= vaccination, FU= follow-up (follow-up time is counted as time after the last vaccination); AE = adverse events, i.e., undesirable medical events; SAE = severe adverse events, i.e., serious undesirable medical events; SUSAR = suspected unexpected severe adverse reaction, i.e., suspected, unforeseen, serious undesirable reactions (SUSAR). Footnote.

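### Injection-site bleeding, which section 5.8.3 singles out as possibly worse with coagulopathy or anticoagulants, is specifically assessed for only 15 or 30 minutes per dose, against 7 days for pain, redness and swelling

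*Combined protocol and SAP*

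**What the plan says.** Section 5.8.3 describes how local reactions are collected. For three of them, "The occurrence of pain, redness, and swelling at the injection site is reported in a diary completed by the patient", from each vaccination until 7 days afterwards. Bleeding is handled differently: "Local bleeding is observed by staff after injection during the observation period". People who have trouble with the diary are telephoned on days 2 and 7.

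The schedule (Table 2, overview of study design) has a row for the "15/30 min post-vaccination observation period" at day 0 and day 21. Section 5.6.3 gives people with bleeding disorders at least 30 minutes and adds: "Other study participants will be observed for at least 15 minutes after vaccination". Section 5.3.1 extends the 30 minutes to people on anticoagulants or otherwise at raised bleeding risk.

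The same part of 5.8.3 expects local reactions to be no more frequent or severe in immunosuppressed people, then qualifies this: "An exception may be local bleeding at the injection site, due to existing medical conditions with coagulopathy or anticoagulant treatments".

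Section 5.5.3 takes the diary content from 5.8.3 and states: "A reactogenicity event recorded in the diary will not be recorded as an AE unless it meets the criteria for an SAE". Section 6.3.3 reports the number and proportion with local reactions in the full analysis set and compares them with the control group.

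**The concern.** The one local reaction that the plan thinks may be worse is the one it prompts for over the shortest time. Section 5.8.3 gives a reason for following the other three for 7 days (onset usually within two days). It gives none for ending the specific assessment of bleeding when the participant leaves.

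Any gap would fall mainly on a subset of patients. People whose bleeding risk can be managed are eligible (5.1.4), while controls must have no significant co-morbidity (5.1.3). Sections 2.2 and 3.2 already expect that reactions may be milder in patients. A low bleeding count could then be read as reassurance, although nobody was asked about bleeding by name after the stay.

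**Working it through.** The plan gives no figure to reproduce. The check compares the assessment windows and then looks for any other place where bleeding is asked about.

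**1. Length of specific assessment, two doses.**
- Bleeding (5.6.3, 5.3.1, Table 2): 2 × 15 min = 30 min, or 2 × 30 min = 60 min. Both are minimums.
- Pain, redness and swelling (5.8.3): 2 × 7 days = 14 days.

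**2. Which observation period is meant.** Sections 5.5.2 and 5.9.1 use similar words for the adverse event collection period, up to 14 days after each dose. In 5.8.3, however, staff do the observing, directly after the injection, and the schedule row gives 15/30 minutes. The short stay is the natural reading.

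**3. Other places where bleeding could be asked about.**

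| Route | Names bleeding? |
|---|---|
| 7-day diary (5.8.3, 5.5.3) | Not among the listed items |
| Day 2 and day 7 calls (5.8.3) | They replace the diary and have no item list; absence is inferred |
| Diary review, day 10 and 2 weeks after dose 2 (5.2.3, 5.2.5) | No; covers local and systemic reactogenicity in general |
| Adverse event review, day 10, day 21 and 2 weeks after dose 2 (5.2.3 to 5.2.5) | No |
| App pictures of the injection site (5.3.3) | No; only when needed |
| Symptom-driven examination (5.5.5) | No |

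**4. Timing of the scheduled reviews.**
- After dose 1: 10 ± 3 = 7 to 13 days, for both diary and adverse events. The next adverse event review is at 21 ± 3 = 18 to 24 days.
- After dose 2: 14 ± 3 = 11 to 17 days, for both.

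**5. What happens to a later bleed that is reported.** It can go on the adverse event form up to 14 days after each dose (5.9.1). Under 5.8.1, "Each incident should be classified by the investigator as mild, moderate, or severe". Under 5.8.2, "AEs suspected of being related to the investigational medicinal product will be followed up until the research subject has recovered". The record is adequate once a bleed is reported; what is missing is the prompt.

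**6. Where the short window falls.** For participants on NOAC treatment, 5.3.1 places the vaccination close to the next dose and then requires at least two hours before that dose is taken. Someone who stays the minimum 30 minutes leaves at least 120 − 30 = 90 minutes before anticoagulant dosing resumes. About ten minutes of the stay are spent under compression. That bleeding or bruising may appear later is a clinical inference; the documents give no onset times for it.

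**The case against.** The strongest reply is that later bleeding is not lost. Staff review the diary for local reactogenicity after each dose, adverse events are reviewed three times, and pictures and examinations are available. A bleed reported by any of these routes can be graded, assessed for causality and followed up. This stands, and it rules out the reading that bleeding after the stay goes uncollected.

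Several other points also stand:
- **Grading scale.** The printed local scale has no bleeding row, but this is weak evidence. The companion systemic scale omits fever, chills, muscle pain and joint pain, all of which 5.8.3 makes diary items. The point therefore rests on the diary list and the staff-observation sentence.
- **Diary rule in 5.5.3.** A reader might infer that it keeps bleeds off the adverse event form. It applies to events recorded in the diary, and bleeding is not a listed diary item. A haematoma entered as swelling would still count as a local reaction; only its cause would be lost.
- **Underlying-disease exception in 5.7.1 and 5.9.1.** A reader might infer that it removes bleeding due to coagulopathy. An injection-site bleed is not a worsening of the underlying disease, and the text does not settle the matter.
- **Scope.** The exception concerns coagulopathy and anticoagulants, not immunosuppressed patients in general. Contraindicating bleeding risk is excluded (5.1.4), and 5.3.1 sets out careful preventive measures, which are not in question.

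These replies narrow the point. They do not supply a route that names bleeding after the participant has left.

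**Conclusion.** The point holds as a minor gap in data capture. Bleeding is specifically assessed for at least 15 or 30 minutes per dose, against 7 days for the other three local reactions. Every later route is general, so capture of bleeding is probably less complete.

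The ratio of the windows (15 or 30 minutes out of 10,080 minutes in 7 days, about 0.15% to 0.30%) might be taken as the share of bleeds detected. It is not: it compares lengths of prompting only. The number of participants with coagulopathy or on anticoagulants is not given, and neither is the timing of bleeds, so no amount of under-recording can be stated.

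One component of a descriptive secondary safety endpoint is affected; the primary endpoint is not. The conclusion assumes that the observation period in 5.8.3 is the post-vaccination stay and that the day 2 and day 7 calls follow the diary items. The diary form itself is not in the documents.

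**What to change.** **For any further study doses.** Add one item to the 7-day diary and the day 2 and day 7 calls: *bleeding, bruising or haematoma at the injection site (yes/no, largest diameter, date)*. In 6.3.3, report it as its own row, split by bleeding-risk status. Anticoagulant use can come from the medication lists (Table 2, footnote 4, and Appendix 1). First confirm that they hold it, since 5.5.2 is narrower and records at screening only ongoing drugs for the underlying disease. Coagulopathy needs one new yes/no field, because Appendix 1 does not name it.

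Keep bleeding out of the pooled any-local-reaction comparison with controls; otherwise anticoagulant use would be mixed into a reactogenicity figure. Do not enter a diary-recorded bleed a second time on the adverse event form unless it is serious. Pain, redness and swelling are treated that way, and double entry would raise the adverse event proportion selectively in patients.

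**For doses already given.** The additions to section 2.1 in versions 5.0 and 7.0 already report results at two weeks and up to 12 months after dose 2, so dosing appears to be over and the diary can no longer be changed. Report staff-observed and adverse-event-form bleeds as a separate row. State that bleeding was solicited only during the 15/30-minute stay, and draw no conclusion about later bleeding from a low count.

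**Cost.** A slightly longer diary and one extra field, with no extra visit. For doses already given, one table row and a statement of the limitation.
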